- A) To evaluate the effects of rivaroxaban on plasma markers of coagulation activation, inflammation and markers of endothelial cell activation in SCD patients during the non-crisis, steady state.
- B) To evaluate the effects of rivaroxaban on microvascular blood flow in SCD patients during the non-crisis, steady state.
- C) To evaluate the safety of rivaroxaban in patients with SCD

Hypotheses/Estimates: Our primary hypothesis is that inhibition of factor Xa with rivaroxaban will reduce inflammation, coagulation and endothelial cell activation in patients with SCD.

Title of the Protocol: The effect of factor Xa inhibition, with rivaroxaban, on the pathology of sickle cell disease

Criteria for Evaluation:

Efficacy: Primary Endpoints: *Soluble vascular cell adhesion molecule-1 (VCAM-1) and interleukin-6 (IL-6):* Plasma levels of soluble VCAM-1 and IL-6 will be obtained at Baseline, and then at weeks 2 and 4 during both Treatment Phases. The primary efficacy measure will be a comparison of the difference between the measurements following 4 weeks of treatment with rivaroxaban/placebo and baseline measurements.

Exploratory Endpoints: *Markers of Coagulation Activation, Endothelial Activation, and Inflammation:* We will measure plasma levels of markers of coagulation activation (thrombinantithrombin [TAT] complexes and D-dimer), other markers of endothelial activation (soluble ICAM) and other markers of inflammation (high sensitivity CRP, MPO, IL-2, IL-8, TNFα, sPLA2), at Baseline and then at weeks 2 and 4 during the Treatment Phases.

Microvascular blood flow: We will analyze microvascular blood flow using laser Doppler velocimetry (LDV) assessments of post-occlusive reactive hyperemia (PORH). Measurements will be obtained at baseline and at 4 weeks during the Treatment Phases.

Safety Assessment: We will evaluate patients for treatment-related complications for the duration of the study. Major bleeding complications (any bleeding episode into critical sites, e.g. intracranial bleed, decrease in hemoglobin concentration of at least 2g/dL from baseline or any prolonged bleeding that requires a blood transfusion), and other clinically relevant non-major or trivial bleeding will be recorded. We will also evaluate for episodes of SCD-related events, including acute pain episodes during scheduled follow up visits

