Study Design: This is a randomized, double-blind, placebo-controlled, crossover study of rivaroxaban to evaluate the efficacy and safety of rivaroxaban in SCD. It will be divided into a Screening/Baseline phase, Treatment phase, and Follow-up phase.

Study Population: Thirty two patients with SCD (HbSS or HbS β^0 thalassemia) between the ages of 18 and 65 who meet the eligibility criteria and provide consent to participate in the study, will be randomized in this crossover trial.

Clinical and Laboratory Evaluations: The Screening/Baseline Phase will occur within 28 days of study drug administration and will include: informed consent, a history and physical examination, and clinical laboratory tests including: a complete blood count, routine coagulation studies, routine chemistries to assess liver and renal function chest x-ray, brain MRI/MRA scan and serum or urine pregnancy test (if female, and of child-bearing capacity). During the Treatment Phase, we will also obtain a complete blood count, routine chemistries to assess liver and renal function, and pregnancy test (if female); and prior to the second treatment phase, a repeat history and examination and laboratory studies will be performed, which will serve as a baseline for the second treatment phase. Finally, measurements of microvascular blood flow (assessed non-invasively using laser Doppler velocimetry), endothelial activation (soluble VCAM, soluble ICAM), coagulation activation (TAT and D-dimer) and markers of inflammation (IL-6, high sensitivity CRP, MPO, IL-2, IL-8, TNF α , sPLA2) will be obtained at specified time points during the Baseline, Treatment and Washout/Follow-up Phases. The Follow-up Phase will consist of safety assessments performed four weeks after the final dose of study treatment.

Title of the Protocol: The effect of factor Xa inhibition, with rivaroxaban, on the pathology of sickle cell disease

Sample Size: In a 2x2 crossover design, assuming a correlation of 0.65 for the pre- and posttreatment measures, to detect a difference of 0.245 in the change of log(sVCAM) and 0.475 in the change of log(IL-6) between the rivaroxaban and placebo groups requires a minimum sample size of 15 per sequence (a total sample size of 30) at 80% power and α =0.05. Assuming a 10% dropout rate, a total of 34 patients is required for this study (17 in each sequence).

Randomization: 1:1 randomization to receive rivaroxaban or placebo.

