Safety Assessment: We will evaluate patients for major bleeding complications (any bleeding episode into critical sites, e.g. intracranial bleed, decrease in hemoglobin concentration of at least 2g/dL from baseline or any prolonged bleeding that requires a blood transfusion) and other clinically relevant non-major or trivial bleeding. We will also evaluate for episodes of SCD-related events during scheduled follow-up visits, by employing a systems review, physical examination, vital signs, and routine laboratory tests.

Termination Criteria: Treatment with study drug will be discontinued at any time if the patient: a) withdraws consent; b) develops a major bleeding episode (defined as any bleeding episode into critical sites, e.g. intracranial bleed, decrease in hemoglobin concentration of at least 2g/dL from baseline or any prolonged bleeding that requires a blood transfusion); or if, c) in the judgment of the investigator, continuation of the study drug will be hazardous to the patient. The UNC DSMB will review the protocol following the occurrence of the 1st treatment-related serious adverse event. The study will be terminated at the occurrence of treatment-related serious adverse events, including major bleeding, in up to 3 study participants.

STATISTICAL METHODS

Normally distributed variables will be presented with means and SD, while summary of variables not normally distributed will be presented with medians and ranges or geometric means and SD as appropriate. The main study objective is to examine the difference between the measurements at baseline and following 4 weeks of treatment. We will evaluate the effect of rivaroxaban on the outcome measures by performing a comparison of treatment by visit using paired t-tests subsequently followed by crossover ANOVA model testing to assess the carry-over effect and treatment effect. In addition, when outcome measures are not normally distributed, we will perform appropriate nonparametric tests. The effect of rivaroxaban on various plasma markers and microvascular blood flow will be estimated using a multiple linear regression model. While the study is adequately powered to evaluate the effect of rivaroxaban on soluble VCAM-1 and IL-6, analysis of the effect of rivaroxaban on the other indicated endpoints are exploratory.

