Sample Size Justification: The primary outcome measures are sVCAM-1 and IL-6. Based on our preliminary data in SCD patients, log (sVCAM) and log(IL-6) are normally distributed with SD of 0.49 and 0.95, respectively. In a 2x2 crossover design, assuming a correlation of 0.65 for the pre- and post-treatment measures, to detect a difference of 0.245 in the change of log(sVCAM) and 0.475 in the change of log(IL-6) between the rivaroxaban and placebo groups requires a minimum sample size of 15 per sequence (a total sample size of 30) at 80% power and $\alpha = 0.05$. Assuming a 10% dropout rate, a total of 34 patients is required for this study (17 in each sequence).

Data Management: A standardized set of data collection forms will be designed using the RED Cap system and a secure database will be created. All data will be stored under password protection on a secured server. A data manager will handle all data entry and database security. This individual will work closely with the statistician on database design and quality assurance procedures.

Timeline: We anticipate beginning recruitment in year 2, following studies on rivaroxaban in sickle mice. Recruitment for this clinical study is expected to take up to 36 months. The remaining few months will be dedicated to completing the studies, data analysis and publication.

HUMAN SUBJECTS

Protection of Human Subjects

1. Human Subjects Involvement and Characteristics: This study seeks to evaluate the efficacy and safety of the factor Xa inhibitor, rivaroxaban, in SCD. Thirty two patients with SCD (HbSS or S β^0 thalassemia) that meet the eligibility criteria will be enrolled in a randomized, double-blind, placebo-controlled, crossover trial. At the time of enrollment, all study subjects will be in the non-crisis, steady state. Informed consent will be obtained according to IRB approved procedure. Patients will be closely monitored for adverse events following randomization to the study drug. The primary goal of this study is to evaluate the effect of rivaroxaban on plasma levels of soluble VCAM and IL-6. Furthermore, we will evaluate plasma other markers of endothelial activation (soluble ICAM) and other inflammatory markers (high sensitivity CRP, MPO, IL-2, IL-8, TNF α , sPLA2), coagulation activation (TAT and D-dimer),

assessment of microvascular blood flow using laser Doppler velocimetry and safety as described in the application.

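### The trial is powered on change in log sVCAM-1 and log IL-6, but the endpoint definition and analysis text never put the primary analysis on the log scale

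*Combined protocol and SAP*

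**What the plan says.** **Endpoint.** Under Criteria for Evaluation in the synopsis, the primary endpoints are introduced as concentrations: "Plasma levels of soluble VCAM-1 and IL-6 will be obtained at Baseline, and then at weeks 2 and 4 during both Treatment Phases". The efficacy measure follows: "The primary efficacy measure will be a comparison of the difference between the measurements following 4 weeks of treatment with rivaroxaban/placebo and baseline measurements". Neither sentence says whether the difference is taken on the level or the log scale.

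**Sample size.** Sample Size Justification states that "log (sVCAM) and log(IL-6) are normally distributed with SD of 0.49 and 0.95, respectively". It takes target differences of 0.245 and 0.475 in the change of the logged values, "assuming a correlation of 0.65 for the pre- and post-treatment measures", and concludes that this "requires a minimum sample size of 15 per sequence (a total sample size of 30) at 80% power" with α = 0.05. Ten per cent dropout brings the total to 34. The synopsis repeats the same calculation.

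**Analysis.** Statistical Methods lists paired t-tests, a crossover ANOVA and multiple linear regression. It mentions no transformation for any of them. Geometric means appear only as one option for descriptive summaries. The one rule for skewed outcomes is that "when outcome measures are not normally distributed, we will perform appropriate nonparametric tests".

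**The concern.** The sample size assumes one scale and the analysis text does not commit to it. Three analyses fit the words: change in level by t-test, change in level by rank test, and change in log level. They estimate different things and have different power, and the plan does not say which one is primary. The nonparametric rule makes the choice depend on how the data look.

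The powered effects are ratios on the log scale. A level-scale analysis targets an absolute change, which in skewed data is driven by the few patients with high values. The log SD is 0.95 for IL-6 and 0.49 for sVCAM-1, so IL-6 has more to lose.

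**Working it through.** **Inputs** (Sample Size Justification): log SD 0.49 (sVCAM-1) and 0.95 (IL-6); effects 0.245 and 0.475, each half an SD; correlation ρ = 0.65; N = 30; α = 0.05.

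**Assumptions:** natural logs, lognormal data, a multiplicative drug effect, no period or carry-over effect, and equal correlation among a patient's four measurements. The log base is not stated. The IL-6 quartiles in Table 1 imply natural-log SDs of ln(7.8/2.7)/1.349 = 0.79 and ln(6.5/1.5)/1.349 = 1.09, which bracket 0.95. Base 10 would give about 0.34 to 0.47. The effects are then ratios of exp(−0.475) = 0.62 and exp(−0.245) = 0.78.

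**1. The plan's own figure.** For a single within-patient difference, the SD is SD × √(2(1 − 0.65)): 0.410 for sVCAM-1 and 0.795 for IL-6. The standardised effect is 0.245/0.410 = 0.475/0.795 = 0.598. A crossover t-test (noncentral t, N − 2 df) gives:
- α = 0.025 per endpoint: N = 30, power 81.1%. This matches the plan, although no such split of α is written.
- α = 0.05: N = 26, power at 30 of 88.5%.

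Dropout: 30/0.9 = 33.3, so 34 as stated.

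For a difference of two changes from baseline, which is closer to the endpoint's wording, the SD is 2 × SD × √(1 − 0.65): 0.580 and 1.124. The standardised effect is 0.475/1.124 = 0.423, and power at 30 with α = 0.05 is 60.8%.

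**2. The same IL-6 effect on the level scale.** Put the baseline median at 1.
- Mean m = exp(0.95²/2) = 1.570.
- Variance m²(exp(0.9025) − 1) = 3.614.
- Covariance m²(exp(0.65 × 0.9025) − 1) = 1.968.
- Expected difference (1 − 0.622) × 1.570 = 0.594.
- Single difference: variance 0.622² × 3.614 + 3.614 − 2 × 0.622 × 1.968 = 2.565, SD 1.602. Standardised effect 0.594/1.602 = 0.371, against 0.598 on logs.
- Difference of changes: variance (0.622² + 3) × 3.614 + [(1 − 0.622)² − (0.622² + 3)] × 1.968 = 5.86, SD 2.42. Standardised effect 0.594/2.42 = 0.245, against 0.423 on logs.

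**3. Power at N = 30 for IL-6.** Level-scale values are simulated.

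| Contrast | α | Log, t-test | Level, t-test | Level, rank test |
|---|---|---|---|---|
| Difference of changes, ρ 0.65 | 0.05 | 61% | 31% | 39-42% |
| Single difference, ρ 0.65 | 0.025 | 81% | 51% | 68-72% |
| Single difference, ρ 0.65 | 0.05 | 88.5% | 65% | 79-81% |
| Difference of changes, ρ 0.78 (set for 80% on logs) | 0.05 | 80% | 43% | 56% |
| Single difference, ρ 0.555 (set for 80% on logs) | 0.05 | 80% | 57% | 70% |

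In the rank-test ranges, the lower end is a rank-sum test between sequences and the upper end a signed-rank test within patients.

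Relative loss by t-test runs from (88.5 − 65)/88.5 = 27% to (61 − 31)/61 = 49%. By rank test it runs from (88.5 − 81)/88.5 = 8% to (61 − 39)/61 = 36%. In the first row, a rank-sum test on log changes keeps 57%. Most of the loss therefore comes from subtracting levels, not from ranking.

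**4. sVCAM-1 by t-test.** Difference of changes: 60.8% to 48%, or 80% to 67% when calibrated. Single difference at 0.05: 88.5% to 82%. The relative loss runs from about 7% to about a fifth.

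**The case against.** The best reply is that the plan omits the scale but does not contradict itself. The endpoint wording is neutral, the sample size text in the same synopsis is explicit about logs, and geometric means are allowed. Since the logs are reported as normal, a statistician could log the data and never reach the nonparametric rule. This is a fair reading. It means the level scale is permitted, not prescribed, but it does not remove the choice.

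Two stronger readings are tempting, and the documents do not support them.

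- **That power halves.** This is right only for a t-test on the difference of changes in IL-6 level. The plan steers skewed outcomes away from a t-test. The rank test loses less, the single-difference variance that reproduces N = 30 loses less, and sVCAM-1 does not come near half.
- **That zeros in the group's earlier data rule out logs.** The legible zeros in Table 1 are lower quartiles of IL-8 and interferon-γ. IL-8 is exploratory and interferon-γ is not a trial endpoint. The IL-6 lower quartiles are 2.7 and 1.5 pg/mL, sVCAM-1 is not in the table, and log(IL-6) is reported as normal. Quartiles cannot exclude a lower IL-6 zero, but none is shown. The documents give no assay limit, so any loss from an assay floor would rest on an assumed one.

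**Conclusion.** The point holds as an unfixed analysis scale for both primary endpoints. In every model examined, moving IL-6 from log change to level change lowers power at 30 completers: by 27% to 49% in relative terms with a t-test and by about 8% to 36% with a rank test. The sVCAM-1 loss is modest. These sizes depend on the assumptions listed with the calculation, above all natural logs and a multiplicative effect, and on which variance model the sponsor meant.

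The 61% starting value is a separate matter. It comes from the variance of a difference of two changes and would remain on the log scale, so it should not be counted as part of the scale loss.

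This should be fixed because the plan's own premise already favours the log scale and fixing it costs nothing.

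**What to change.** In Criteria for Evaluation and in Statistical Methods, state that both primary endpoints are analysed as change in natural-log plasma level in the crossover model and reported as a rivaroxaban/placebo geometric mean ratio with its confidence interval. State that rank tests are sensitivity analyses only, preferably on the log changes, and that a normality check does not change the primary analysis.

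Optionally, add a rule that values below an assay's limit are treated as censored at that limit and not entered as 0. This matters mainly for exploratory IL-8.

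The cost is a few sentences, with no extra patients, visits or samples.

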To determine if the intrinsic coagulation pathway contributes to the hypercoagulable state in SCD, we treated sickle cell mice with an antibody called 14E11 (kindly provided by Dr. [name]) that blocks activation of the intrinsic coagulation pathway by inhibiting FXIa generation. We observed that 24 hours after injection of 14E11 (4 mg/kg) the aPTT was significantly increased and plasma TAT was significantly reduced in BERK mice. We did not measure other parameters due to the short time period of this experiment (1 day). The mechanism of FXIa activation is not known and will not be pursued in this proposal. It is possible that polyphosphates released from activated platelets may activate FXII {Smith, 2006} {Muller, 2009}.

Measurements of coagulation activation, EC activation and cytokine expression in sickle cell patients.

Our group has had a long-term interest in coagulation activation in patients with SCD{Ataga, 2008 #292; Ataga, 2007 #272; Key, 1998 #269}. In a study of 76 patients with SCD and 6 healthy, control subjects of African descent, SCD patients had significantly higher D-dimer levels than control subjects (1251.5 ng/mL [FEU] *vs.* 318 ng/mL [FEU]; p = 0.02) {Ataga, 2008}. The median values of TAT and F1+2 levels were also higher in SCD patients, although the differences were not statistically significant.

In another study of 64 SCD patients, we observed a correlation between TAT and lactate dehydrogenase (r = 0.57, p < 0.0001) (Figure 1A), with borderline correlations between TAT and total bilirubin (r = 0.25; p = 0.054), indirect bilirubin (r = 0.26, p = 0.051), and hemoglobin (r =- 0.24; p = 0.071) {Ataga, 2012}. TAT was also correlated with the absolute monocyte count (r = 0.27; p = 0.035) and NT-proBNP (r = 0.35; p = 0.005). Similarly, D-dimer was correlated with lactate dehydrogenase (r = 0.56; p < 0.0001) (Figure 1B), indirect bilirubin (r = 0.26; p = 0.048), hemoglobin (r = -0.32; p= 0.012), NT proBNP (r = 0.42; p < 0.0001), with borderline correlations with absolute monocyte count (r = 0.23; p = 0.074). Both TAT (r = 0.37; p = 0.004) and D-dimer (r = 0.49; p < 0.0001) (Figure 2) were correlated with soluble VCAM-1. When the analyses were limited to only patients with SS/SD/S β^0 thalassemia. there was a significant correlation between TAT and lactate dehydrogenase (r = 0.62, p < 0.0001), indirect bilirubin (r =0.296, p = 0.044), and NT-proBNP (r = 0.32, p = 0.026), with borderline correlation with total bilirubin (r = 0.28, p =(0.053) and absolute monocyte count (r = 0.25, p = 0.089). Similarly, we observed significant correlations between Ddimer and lactate dehydrogenase (r = 0.60, p < 0.0001), hemoglobin (r = -0.29, p = 0.039), and fetal hemoglobin (r= -0.31, p = 0.035), NT-proBNP (r = 0.49, p < 0.0001), with borderline correlations with platelet count (r = -0.28, p

= 0.053), total bilirubin (r = 0.24, p = 0.093) and indirect bilirubin (r = 0.26, p = 0.07). Finally, we observed a significant correlation between TAT and D-dimer (r = 0.66; p<0.0001) (Figure 3). However, no correlations were observed between TAT and soluble CD40 ligand (r = 0.016, p = 0.91) or between TAT and MPTF procoagulant activity (r = 0.064, p = 0.63). Similarly, no correlations were observed between D-dimer and soluble CD40 ligand (r = -0.17; p = 0.19) or between D-dimer and MPTF procoagulant activity (r = 0.11, p = 0.40).

Plasma markers of coagulation activation are associated with clinical complications in SCD.

The level of TAT was significantly higher in patients with a history of retinopathy compared to those without this complication (6.05 ng/L; IQR, 4.91, 10.98 ng/L vs. 4.52 ng/L; IQR, 3.22, 7.33 ng/L, p=0.023). In addition, the level of TAT was lower in patients on hydroxyurea therapy compared to those not on such therapy (4.39 ng/L; IQR, 3.25, 8.77 ng/L vs. 6.5 ng/L; IQR, 5.08, 8.76 ng/L, p =0.044). D-dimer appeared to be associated with a history of stroke (3003.1 ng/mL [FEU]; IQR, 1513, 3067 ng/mL [FEU] vs. 1399.5 ng/mL [FEU]; 648.8, 2217 ng/mL [FEU], p = 0.062), although the difference was not statistically significant. When those patients with a measurable tricuspid regurgitant jet velocity were evaluated (N = 43), there was no significant correlation between D-dimer and tricuspid regurgitant jet velocity (r =0.25, p = 0.10). However, when the analyses were limited to patients with SS/SD/S β^0 thalassemia, we observed associations between D-dimer and a history of thrombotic stroke (3035.2 ng/mL [FEU]; IQR 2559, 3494 vs. 1269.6 ng/mL [FEU]; IOR 688.4, 2347, p = 0.049), TAT and history of retinopathy (7.145 ng/L; IOR 5.225, 12.01 vs. 4.465 ng/L; IOR 3.215, 7.332, p = 0.018). There appeared to be a correlation between tricuspid regurgitant jet velocity and D-dimer (r = 0.3, p = 0.067), although this was not statistically significant. Although no significant correlation was observed between plasma markers of thrombin generation and echocardiography-derived TRV, TRV may not be particularly sensitive for the diagnosis of PHT {Parent, 2011}. As right heart catheterizations were not obtained in all of the study subjects it is uncertain how many patients truly have PHT. However, as NT-proBNP is a surrogate for PHT {Machado, JAMA; Ataga, 2006}, the correlation between NT-proBNP and both D-dimer and TAT (see #3 above) suggests a likely association between these markers of thrombin generation and RHC-diagnosed PHT.

Correlation of inflammatory cytokines with echocardiography-defined pulmonary hypertension.

Levels of selected inflammatory cytokines were measured in 56 HbSS patients to evaluate their association with echocardiography-defined PHT {Ataga, 2008}. Patients with echocardiography-defined PHT had consistently higher median levels of IL-6 (4.7 ng/mL vs. 2.9 ng/mL; p = 0.06), interleukin-8 (5.4 ng/mL vs. 2.7 ng/mL; p = 0.07) and interleukin-10 (0.57 ng/mL vs. 0.35 ng/mL; p = 0.10) compared with HbSS patients without PHT, although the differences were only of borderline statistical significance (Table 1).

Analyte	PHT (N=19) Median (25 th , 75 th)	No PHT (N=34) Median (25 th , 75 th)	p value
Interleukin-6 (pg/mL)	4.7 (2.7, 7.8)	2.9 (1.5, 6.5)	0.06
Interleukin-8 (pg/mL)	5.4 (2.4, 15.5)	2.7 (0, 7.9)	0.07
Interleukin-10 (pg/mL)	0.57 (0.25, 1.2)	0.35 (0.03, 0.82)	0.10
Interferon-γ (pg/mL)	31.3 (0, 85.7)	13.3 (0, 71.4)	0.76
Tumor necrosis factor-α	1.9 (0.7.8)	3.3 (0.98, 21.9)	0.25

Table 1

Laser Doppler velocimetry in SCD.

We conducted a proof-of-principle study to determine whether pentosan polysulfate sodium (PPS) improves baseline blood flow in the microvasculature of patients with SCD {Kutlar, 2012}. PPS has structural and functional similarities to, but considerably less anticoagulant activity than heparin, as well as potent blocking activity against cell adhesion to P-selectin. At the time that this double-blind, placebo-controlled, randomized, multi-center study was discontinued, 19 of 41 enrolled patients had been randomized to the active PPS arm, 14 had received PPS, nine had received PPS for at least eight weeks, and two of the nine disclosed they had not taken their study drug reliably. In the seven evaluable patients, PPS was safe and nontoxic when given for 8 to 12 weeks, and there was a highly significant reduction in plasma soluble VCAM-1 from pretreatment levels ($p \le 0.015$ at 2 wk; p < 0.001 at 8 wk). There also was a non-significant trend toward improved blood flow measured by laser Doppler velocimetry (LDV) in these same seven patients, but no evidence of improved soluble VCAM-1 levels or blood flow in the placebo group. This study demonstrates our experience with the conduct of studies evaluating microvascular blood flow with laser Doppler velocimetry. [name] will serve as a consultant in this application and will be responsible for interpreting the LDV test results.

Anticoagulation with warfarin is safe in SCD.

In a pilot study, we showed that low-intensity anticoagulation with warfarin (INR of 1.5 - 2.0) for 12 months appears safe in appropriately selected patients (unpublished data). There were no bleeding episodes during the course of the study. In addition, the median baseline INR in the 4 patients in the placebo arm was 1.1 (range: 1.0 to 1.1) and following treatment was 1.1 (range: 1.0 to 1.2). The median baseline INR for the 3 patients in the low-intensity anticoagulation arm was 1.1 (range: 1.0 to 1.1) and following treatment was 1.7 (range: 1.4 to 1.9). Following treatment, patients on low-intensity anticoagulation had greater reductions in TAT (M_{baseline}= 4 μ g/L, M_{12mth}= 2 μ g/L) and D-dimers levels (M_{baseline}= 971 ng/mL, M_{12mth}= 513 ng/mL) compared to patients on placebo who experienced relatively no change in their levels (TAT M_{baseline}= 5.5 μ g/L and M_{12mth}= 5.0 μ g/L; D-dimers M_{baseline}= 1050 ng/mL, M_{12mth}= 871 ng/mL). Finally,

despite concerns of the risk of bleeding in SCD patients, our clinical experience suggests that appropriately selected patients with SCD on standard intensity anticoagulation do not appear to have an increased risk of bleeding.

RESEARCH DESIGN AND METHODS

We will conduct a randomized, double-blind, placebo-controlled, crossover study to evaluate the efficacy and safety of rivaroxaban in SCD. We have selected this agent based on our preliminary data in sickle mice showing that 'upstream' TF inhibition achieves the desired effects on inflammation and endothelial activation, but that 'downstream' thrombin inhibition does not. The study will consist of three phases: 1) Screening/Baseline; 2) Treatment; and 3) Follow-up. The Screening/Baseline Phase will occur within 28 days of study drug administration and will include: informed consent, a history and physical examination, and clinical laboratory tests including: a complete blood count, routine coagulation studies, routine chemistries, chest x-ray, and serum or urine pregnancy test (if female, and of child-bearing capacity). The sequence of drug administration will be generated via block permuted randomization procedure. The 4-week Treatment Phase will consist of drug administration, efficacy assessments and safety assessments (including pregnancy testing in females of child-bearing capacity). After the first treatment period, there will be a washout period of 14 ± 3 days. In the second treatment phase, patients will be crossed over to receive rivaroxaban or placebo, depending on their initial treatment assignment. The total duration of the Treatment phase (including washout) will be 10 weeks. During the Follow-up Phase at week 12, patients will obtain their final study evaluation. Table 2 provides a detailed schedule of assessments for the study period.

Treatment: Subjects will receive rivaroxaban 20 mg/day (the approved dose to prevent stroke and systemic embolism in patients with non-valvular atrial fibrilation) and placebo for 4 weeks each, separated by a 2-week washout phase. Pill counting will be used to assess compliance. PT/INR will be monitored by an unblinded investigator to assess compliance with no other involvement in the study). If major bleeding or other serious adverse event occurs (see Appendix 2), the study drug will be discontinued and the patient followed until resolution of the problem. Subjects that discontinue the study early will not be replaced.

Eligibility Criteria:

Inclusion Criteria:

- a) 18 to 65 years of age;
- b) HbSS or HbS β 0 thalassemia; serum creatinine $\leq 1.0 \text{ mg/dL}$ men) or 1.2 mg/dl (women);
- c) ALT ≤ 2 times upper limits of normal;
- d) platelet count \geq 150,000 cu/mm;
- e) normal baseline PT/INR and aPTT;
- f) be in the non-crisis, "steady state" at enrollment with no severe pain episodes during the preceding 4 weeks;
- g) ability to understand the requirements of the study and be willing to give informed consent;
- h) women of childbearing age must be practicing an adequate method of contraception;
- i) if on hydroxyurea, must be on a stable dose for at least 3 months. The dose of hydroxyurea will not be adjusted during the study duration except for safety reasons.

Exclusion Criteria:

- a) hypersensitivity to any component of rivaroxaban;
- b) history of major GI bleeding or bleeding diathesis;
- c) baseline Hb < 5.5 g/dL;
- d) history of clinically overt stroke;
- e) brain MRI/MRA scan with evidence of Moya Moya;
- f) pregnant or breastfeeding;
- g) active liver disease or ALT > 3 times upper limit of normal;
- h) on chronic anticoagulant, NSAID or statin therapy;
- i) history of metastatic cancer;
- j) current alcohol abuse;
- k) on a chronic transfusion program or any blood transfusion in the prior 3 months;
- 1) ingested any investigational drugs within the past 4 weeks
- m) use of CYP3A4/P-glycoprotein inducers such as carbamazepine, phenytoin, rifampin, and St John's wort;
- n) use of CYP3A4/P- glycoprotein inhibitors such as ketoconazole, indinavir/ritonavir, itraconazole, lopinavir/ritonavir, ritonavir, and conivaptan

Assessments: Activation of coagulation.: Plasma levels of TAT and D-dimer measured using a commercially available ELISA kit at baseline, and at 2 and 4 weeks following initiation of study drug

Endothelial cell activation: Plasma levels of soluble VCAM-1 and soluble ICAM-1 measured using a commercially available ELISA kit at baseline, and at 2 and 4 weeks following initiation of study drug

Inflammatory markers: Plasma levels of IL-6 (commercially available ELISA), high sensitivity CRP, MPO, IL-2, IL-8, TNFα, sPLA2 (multiple cytokine assay using Luminex MAP technology; UNC core facility) at baseline, and at 2 and 4 weeks following initiation of study drug

Microvascular blood flow: We will analyze microvascular blood flow using laser Doppler velocimetry (LDV) (Perimed, PF5001, Stockholm, Sweden) assessments of post-occlusive reactive hyperemia (PORH). Measurements will be obtained at baseline and at 4 weeks following initiation of therapy.

Safety Assessment: We will evaluate patients for major bleeding complications (any bleeding episode into critical sites, e.g. intracranial bleed, decrease in hemoglobin concentration of at least 2g/dL from baseline or any prolonged bleeding that requires a blood transfusion) and other clinically relevant non-major or trivial bleeding. We will also evaluate for episodes of SCD-related events during scheduled follow-up visits, by employing a systems review, physical examination, vital signs, and routine laboratory tests.

Termination Criteria: Treatment with study drug will be discontinued at any time if the patient: a) withdraws consent; b) develops a major bleeding episode (defined as any bleeding episode into critical sites, e.g. intracranial bleed, decrease in hemoglobin concentration of at least 2g/dL from baseline or any prolonged bleeding that requires a blood transfusion); or if, c) in the judgment of the investigator, continuation of the study drug will be hazardous to the patient. The UNC DSMB will review the protocol following the occurrence of the 1st treatment-related serious adverse event. The study will be terminated at the occurrence of treatment-related serious adverse events, including major bleeding, in up to 3 study participants.

STATISTICAL METHODS

Normally distributed variables will be presented with means and SD, while summary of variables not normally distributed will be presented with medians and ranges or geometric means and SD as appropriate. The main study objective is to examine the difference between the measurements at baseline and following 4 weeks of treatment. We will evaluate the effect of rivaroxaban on the outcome measures by performing a comparison of treatment by visit using paired t-tests subsequently followed by crossover ANOVA model testing to assess the carry-over effect and treatment effect. In addition, when outcome measures are not normally distributed, we will perform appropriate nonparametric tests. The effect of rivaroxaban on various plasma markers and microvascular blood flow will be estimated using a multiple linear regression model. While the study is adequately powered to evaluate the effect of rivaroxaban on soluble VCAM-1 and IL-6, analysis of the effect of rivaroxaban on the other indicated endpoints are exploratory.

Sample Size Justification: The primary outcome measures are sVCAM-1 and IL-6. Based on our preliminary data in SCD patients, log (sVCAM) and log(IL-6) are normally distributed with SD of 0.49 and 0.95, respectively. In a 2x2 crossover design, assuming a correlation of 0.65 for the pre- and post-treatment measures, to detect a difference of 0.245 in the change of log(sVCAM) and 0.475 in the change of log(IL-6) between the rivaroxaban and placebo groups requires a minimum sample size of 15 per sequence (a total sample size of 30) at 80% power and $\alpha = 0.05$. Assuming a 10% dropout rate, a total of 34 patients is required for this study (17 in each sequence).

Data Management: A standardized set of data collection forms will be designed using the RED Cap system and a secure database will be created. All data will be stored under password protection on a secured server. A data manager will handle all data entry and database security. This individual will work closely with the statistician on database design and quality assurance procedures.

Timeline: We anticipate beginning recruitment in year 2, following studies on rivaroxaban in sickle mice. Recruitment for this clinical study is expected to take up to 36 months. The remaining few months will be dedicated to completing the studies, data analysis and publication.

HUMAN SUBJECTS

Protection of Human Subjects

1. Human Subjects Involvement and Characteristics: This study seeks to evaluate the efficacy and safety of the factor Xa inhibitor, rivaroxaban, in SCD. Thirty two patients with SCD (HbSS or S β^0 thalassemia) that meet the eligibility criteria will be enrolled in a randomized, double-blind, placebo-controlled, crossover trial. At the time of enrollment, all study subjects will be in the non-crisis, steady state. Informed consent will be obtained according to IRB approved procedure. Patients will be closely monitored for adverse events following randomization to the study drug. The primary goal of this study is to evaluate the effect of rivaroxaban on plasma levels of soluble VCAM and IL-6. Furthermore, we will evaluate plasma other markers of endothelial activation (soluble ICAM) and other inflammatory markers (high sensitivity CRP, MPO, IL-2, IL-8, TNF α , sPLA2), coagulation activation (TAT and D-dimer),

assessment of microvascular blood flow using laser Doppler velocimetry and safety as described in the application.

2. Sources of Research Material: Enrollment and study participation will involve the collection of a full range of clinical data, including medical history. We will obtain clinical and laboratory data as well as assessments of microvascular blood flow at specified intervals during the course of the studies as described in the research plan.

3. Plans for Recruitment: Patients will be recruited from amongst the patients that routinely receive their care at the UNC Comprehensive Sickle Cell Program. [name] and/or one of the co-investigators will discuss the studies with all eligible patients. Interested patients will be provided with a copy of the consent form(s), and the study coordinator or PI (or a co-investigator) will carefully go over the consent with each candidate before he/ she signs. We will strive to ensure that all patients understand the nature of the study and all their questions will be answered. The original consent form will be placed in the study files, in a secure, locked cabinet. Potential subjects will be contacted during regularly scheduled clinic visits, but may be contacted at home by study personnel if they are known to meet the eligibility criteria. The PI and study nurse involved in the study are regular staff of the program. Samples obtained from patients specifically for these studies will be collected as approved by the IRB. This is anticipated to occur during specified study visits.

4. Potential Risks: The study entails physical risk associated with venipuncture to obtain blood samples; administration of rivaroxaban; and pneumatic occlusion cuff placed around the arm to a suprasystolic pressure (~ 200 mmHg) during the assessment of microvascular blood flow. The most significant risks of blood tests are discomfort and bruising. There is still limited clinical experience with the use of rivaroxaban in the general population, and even less so in SCD. However, published studies indicate that the most common complications of rivaroxaban are bleeding, bruising, peripheral edema, dizziness, headache, pyrexia, fatigue, syncope, pruritus, rash, blister, diarrhea, thrombocytopenia, extremity pain, and back pain. Pneumatic occlusion of the arm to a suprasystolic pressure is uncomfortable. However, this technique has been safely performed in SCD patients. Patients will be monitored very closely for any laboratory or clinical complications during the course of the studies.

